Individuals who complete the baseline assessment and meet all inclusion/exclusion criteria will be randomly assigned to one of the two intervention groups: MTcap (N=28) or SGT+CBTI (N=28). Both interventions are described below. Randomization procedures will follow the CONSORT criteria for randomized trials. Stratified randomization will be used to ensure that both groups are balanced in baseline hypnotic drug type half-life (i.e., temazepam/zolpidem; alprazolam/lorazepam; clonazepam) and gender. The study statistician will generate the stratified randomization sequence. A set of envelopes containing the group assignment will be generated and stored in a secure file drawer accessible only authorized staff. Once final eligibility is determined, the data manager will open the next envelope in sequence within the appropriate stratum.

Interventions

Both interventions will involve 8 sessions provided by a trained cognitive behavioral therapy for insomnia (CBTI) interventionist. The intervention period is expected to last approximately 9 weeks (but may be extended as described below). Both interventions include a tapering protocol for benzodiazepine use, behavioral therapy for insomnia, plus weekly assessment for withdrawal symptoms (see table below).

Week	Session	Basic Components Groups A & B	Time
1	1	Education + sleeping medication taper + side-effect monitoring	60 minutes
2	2	Education + sleeping medication taper + side-effect monitoring	60 minutes
3	3	Education + sleeping medication taper + side-effect monitoring	60 minutes
4	4	Education + sleeping medication taper + side-effect monitoring	60 minutes
5	5	Education + sleeping medication taper + side-effect monitoring	60 minutes
6	6	Education + sleeping medication taper + side-effect monitoring	60 minutes
7		Side-effect monitoring only	20 minutes
8	7	Education + sleeping medication taper + side-effect monitoring	60 minutes
9 Beginning of week		Side-effect monitoring only	20 minutes
9 End of week	8	Education + sleeping medication taper + side-effect monitoring	60 minutes

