Daily sleep and habits diary: Participants will use the diary to record bedtime, wake time, total sleep time, time to fall asleep, time awake at night, number of awakenings, napping, exercise, caffeine/alcohol/tobacco use. Participants in the MTcap group only will also record their perceived hypnotic dose taken and their daytime function and sleep quality.

MTcap (Masked Taper plus cognitive behavioral therapy-augmented program):

- a. **Hypnotic taper protocol:** Participants will receive encapsulated hypnotics in a blister taper pack prepared by a compounding pharmacy. Participants will be informed that gradual dose reduction will occur during the program, but they will be blinded to the actual dose they receive each day. The planned rate of reduction of hypnotic will be about 25% per week. The final taper pack will consist of 4 placebo capsules (nights 1-4) and 3 empty blisters (nights 5-7). This planned rate of taper would yield a taper length similar to those reported in other studies, where the average length of taper was 49 days (range 6.5 to 84 days).
- b. **Cognitive behavioral therapy for insomnia-augmented program:** The 8 sessions will incorporate the key components of CBTI (sleep restriction, stimulus control, cognitive restructuring, targeted sleep hygiene) and CBT targeting hypnotic withdrawal. Using the masked doses as a CBT tool, we will add exercises and concepts designed to address and alter expectations for hypnotics. A daily sleep/perceived hypnotic dose diary will be used as a tool for challenging expectancies about hypnotics, refining treatment recommendations, and adjusting the weekly plan. At the last session, the interventionist will inform MTcap participants of the actual doses that they were taking over the 9-week intervention. Participants will be given the taper schedule that the SGT+CBTI group followed unless there was a plateau in the tapering, in which case participants will be shown a revised taper schedule. The interventionist will tell participants the dose that they are currently taking and will review the last week's sleep diary to compare what participants thought they were taking with the actual dose. A study physician will also be available if the participant has specific medical or pharmacological questions about the taper.

SGT+CBTI:

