- a. **Hypnotic taper protocol:** Participants will receive hypnotics in a traditional medication container prepared by a contracted compounding pharmacy. Participants will also receive a printed taper schedule (see attached Taper Schedule) that reduces the hypnotic using the same schedule as the MTcap group. Each participant will be given a pill cutter so they can cut pills in half or into quarters as directed. A printed taper schedule is routinely used in clinical practice to assist patients in reducing hypnotic use. An exception to this protocol will occur if the prescribed medication is temazepam. This medication only comes in capsule form, so it cannot be cut into halves or quarters. Consequently, the participant will receive two difference strengths of temazepam (e.g., 15mg and 7.5mg) in two separately labeled bottles. Rather than cutting the higher strength capsule in half,

participants will take the lower strength capsule. This is the taper method that is used clinically for temazepam.

b. **Cognitive behavioral therapy for insomnia:** Participants will receive standard CBTI (i.e., stimulus control, sleep restriction, targeting maladaptive beliefs about sleep, sleep hygiene, and relaxation techniques), and will not be provided with the extra exercises and tools that the MTcap group will receive. The sleep diary that participants will complete will be slightly different from the MTcap sleep diary.

Modified taper plans

We have identified specific situations when the taper plan may need to be modified:

a) Withdrawal symptoms/extended taper required:

The taper may be extended up to a maximum of 16 weeks if the participant has withdrawal symptoms or cannot tolerate the scheduled taper, based upon changes in several of the CIWA-B items and vital signs, along with the patient's, interventionist's, and study physicians' judgments. In the MTcap group, an extended taper may be achieved by giving a duplicate 7-day blister pack (e.g., plateauing the doses until the participant is ready to move to the next blister pack). In the SGT+CBTI group, participants will be instructed to repeat a particular week in the printed taper schedule. Participants will continue to be monitored with weekly CIWA-B, vital signs, and the interventionist will review and reinforce key content of the intervention.

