For the SGT+CBTI (supervised gradual taper + CBTI) group, the paper taper schedule will indicate which days of the week the participant should and should not take the hypnotic. For example, Mondays, Wednesdays, Fridays, and Saturdays may be deemed drug days, while Tuesdays,

Thursdays, and Sundays may be deemed drug-free days. The gradual tapering of drug doses on the drug days will occur over the two-month period. The drug-free days will be clearly marked on the taper schedule. A progressive increase in the number of drug-free days will occur during the taper.

c) More than 1 hypnotic at baseline: Participants who use >1 of the target hypnotics will be tapered off the targeted hypnotics simultaneously using two different blister packs.

Protocols for preparation of hypnotics

MTcap group: The blister packs containing the hypnotic will be prepared by a contracted compounding pharmacy experienced in preparing medications for research purposes. [name] or [name] will use California tamper resistant prescription forms for controlled substances to write a prescription for the appropriate hypnotic that will cover the entire intervention period. The prescriptions will be sent via encrypted email or fax to the pharmacy. The compounding pharmacy will prepare the blister packs for the intervention period (e.g., 8 weeks, but could be longer if the participant needs a prolonged taper) and send them via overnight mail or courier to the UCLA Research Pharmacy. If necessary, the medications will be picked up by research staff and transported to the Research Pharmacy. The research pharmacist will label the blister packs per UCLA protocols. The medication information will be entered into CareConnect (not as an active order) as “[medication name] study material Week [enter #]”.

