Potential benefits to society: Hypnotic discontinuation is of critical importance to older adults. Clinical guidelines and professional groups recommend that older patients not be prescribed benzodiazepines and z-drugs, and in the context of insomnia, effective non-pharmacological treatments for insomnia are available. This study has the potential to boost hypnotic discontinuation rates. In addition, the study may provide new insight into the placebo effect. The ultimate goal of this line of research is to implement a program that can reduce hypnotic use long-term in older patients with current or past insomnia.

Potential risks/discomforts:

Benzodiazepine withdrawal symptoms: Symptoms are not common with withdrawal of low doses of benzodiazepines, but could include dizziness, anxiety, depression, and insomnia. The proposed intervention has a similar risk level to behavioral/ pharmacological strategies recommended by healthcare providers to adults as part of routine clinical care. Based on our pilot data and our team's collective clinical experience with low-dose hypnotic discontinuation, withdrawal symptoms that warrant protocol changes are uncommon. To reduce the risk of severe withdrawal symptoms, adults at high risk of complicated withdrawal or on high benzodiazepine doses (based on comorbidities, current prescriptions, and answers to assessment questions) will not be randomized to receive the intervention. Participants will be monitored weekly with the Clinical Institute Withdrawal Assessment-Benzodiazepine [CIWA-B] instrument and with weekly vital signs. If the participant is found to have mild symptoms of withdrawal based on select items from the CIWA-B or on mild changes in vital signs, a study physician (e.g., Drs. [name] or [name]) and the participant may decide to plateau the taper until the participant is ready to continue with the dose taper. If participants are found to have moderate, severe, or very severe scores on select items in the CIWA-B, moderate or severe vital sign changes, or have worsening severe insomnia, the study physicians will discuss the patient's symptoms with a staff psychiatrist to determine whether changes to the taper schedule are needed (including increasing or plateauing the dose) and whether the patient needs additional clinical evaluation. If the patient needs immediate clinical evaluation, the participant will be escorted to the outpatient clinic or for life-threatening emergencies at our facility, we will call 911.

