
Confusion about duplicate hypnotic prescriptions: Participants may not understand that the hypnotic provided by the study (in blister packs or medication bottle) replaces the hypnotic that they were previously taking. This could result in participants taking both prescriptions at the same time, which would result in a higher dose than prescribed, and possible side-effects (e.g., daytime sleepiness, dizziness). To avoid confusion about duplicate hypnotic prescriptions, participants in both groups will be asked to bring all their medications to the first intervention session. The interventionist will identify the hypnotic that will be tapered and will place the bottle in a zip-locked plastic bag with a secure plastic tie. A label will be affixed to the outside of the plastic bag that states, "Do not take this medication during the 9-week SWITCH study unless instructed by the study staff." The interventionist

will explain that the participant will receive the same hypnotic either in a new medication bottle or in the blister packs and should put the old prescription in the plastic bag in a safe location.

Increased daytime sleepiness: Adjustments to the participant's sleep habits may result in some initial daytime sleepiness. Daytime sleepiness will be monitored during each weekly in-person intervention assessment with the Epworth Sleepiness Scale, and participants with increased daytime sleepiness will be counseled on the possibility of impaired cognition and increased fall and motor vehicle crash risk. If excessive daytime sleepiness is thought to be due to study-related sleep restriction (as opposed to, for example, a newly-prescribed medication from the individual's physician), the prescribed sleep schedule will be adjusted.

Mental discomfort: The minor risks associated with completion of the questionnaires include tediousness, fatigue, and/or mental discomfort answering the items. Participants could also find wearing the actigraph and WatchPAT device to be annoying or uncomfortable. To reduce the risk of mental discomfort among participants, research staff will be trained to recognize discomfort in participants, and they will be trained to remind participants of the voluntary nature of the research and the option for participants to decline participation in any portion of the research project.

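### The warning label on the participant's own hypnotic covers a 9-week study, but the taper may run to 16 weeks; tie the label to the study taper

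*Combined protocol and SAP*

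**What the plan says.** The paragraph on duplicate hypnotic prescriptions, under Benefits and Risks, recognises that a participant might take their own supply as well as the study's. It names the results: too high a dose, daytime sleepiness and dizziness. At the first session the interventionist "will place the bottle in a zip-locked plastic bag with a secure plastic tie", and the label on the bag reads "Do not take this medication during the 9-week SWITCH study unless instructed by the study staff". The interventionist also explains that the study supply replaces the old one, which should be stored safely.

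Elsewhere the duration is open. The Interventions section says "The intervention period is expected to last approximately 9 weeks (but may be extended as described below". Modified taper plans, item a, says "The taper may be extended up to a maximum of 16 weeks if the participant has withdrawal symptoms" or cannot tolerate the schedule, and gives a way of extending it in each arm. Under Protocols for preparation of hypnotics, the pharmacy makes up the MTcap "blister packs for the intervention period (e.g., 8 weeks, but could be longer if the participant needs a prolonged taper". The telehealth addendum supplies remote MTcap participants with scheduled packs and an equal number of plateau packs, in three deliveries. The last scheduled pack is inert: "The final taper pack will consist of 4 placebo capsules (nights 1-4) and 3 empty blisters (nights 5-7".

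During an extension, weekly withdrawal scores and vital signs continue and "the interventionist will review and reinforce key content of the intervention". Benefits and Risks also states that "withdrawal symptoms that warrant protocol changes are uncommon". No section mentions replacing or rewording the label when a taper is extended.

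**The concern.** The label is the written control that stays on the old bottle at home, and its stated period is shorter than the taper that the same protocol permits. Tapers are extended for people with withdrawal symptoms or poor tolerance of the schedule, so a participant in, say, week 11 is still taking study medication while the label names a 9-week period. An MTcap participant is also masked to dose and could not tell how much active drug an old tablet would be added to.

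What is at stake is the hazard that the protocol itself names, in adults over 55. The trial's estimates, power and analysis are not affected.

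**Working it through.** The plan gives no figure of its own to reproduce. The check compares the durations in the text.

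**Inputs**
- Label period: 9 weeks (Benefits and Risks).
- Longest taper: 16 weeks (Modified taper plans, item a).
- Scheduled MTcap packs: 3 + 3 + 2 = 8 (addendum, Getting Materials/Medications to Randomized Participants). This agrees with the 8-week example under Protocols for preparation of hypnotics.
- Plateau packs: 3 + 3 + 2 = 8 (same list). 8 + 8 = 16, which matches the maximum.
- Active scheduled packs: 8 − 1 inert final pack = 7. The MTcap taper paragraph likens its length to an average of 49 days, and 49 / 7 = 7 weeks, which is consistent.

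**Assumptions.** Packs run consecutively from session 1, the label's period is counted from the same point, and every scheduled pack except the last holds some active drug.

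**Step 1: no repeats.** The taper takes 8 weeks, inside the 9-week wording.

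**Step 2: taper weeks after week 9, with r repeated weeks.** max(0, 8 + r − 9) = max(0, r − 1). For r = 1 this is 0; for r = 2 it is 1; for r = 8 it is 7, the same as 16 − 9. The gap opens at the second repeated week.

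**Step 3: active-drug MTcap weeks after week 9, with k repeated active packs.** max(0, 7 + k − 9) = max(0, k − 2).

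| k | 0 to 2 | 3 | 4 | 5 | 6 | 7 | 8 |
|---|---|---|---|---|---|---|---|
| Active weeks after week 9 | 0 | 1 | 2 | 3 | 4 | 5 | 6 |

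Active drug passes week 9 from the third repeated active week.

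**Step 4: ceiling.** If each scheduled pack is duplicated once, as the matched supply suggests, there are 7 × 2 = 14 active and 2 inert packs. Then 14 − 9 = 5 weeks, and 5 / 16 = 31% of the longest taper. If all eight extra weeks repeat active packs, 7 + 8 = 15 are active. Then 15 − 9 = 6 weeks, and 6 / 16 = 38%.

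**Step 5: the other arm.** SGT+CBTI follows the same reduction schedule, so the Step 2 threshold should carry over. Its printed schedule is not in the document, so the active-week count is given for MTcap only.

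**Number affected.** The document gives no rate of extended tapers, so this cannot be computed.

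**The case against.** There is a fair case that this hardly matters. The protocol uses nine weeks as shorthand for the intervention even where it allows for a plateau, as in the MTcap paragraph on disclosing doses at the last session. The label carries no expiry date, and a participant may take the phrase as the study's name. The spoken instruction to keep the old supply bagged and safe has no end date.

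An extension also cannot happen unnoticed. A study physician is involved in decisions to plateau, SGT+CBTI participants are told to repeat a week, and video MTcap participants show the duplicate pack to the interventionist. Confusion over replacement is likeliest at the switch in session 1, when the label is plainly in force, and late doses would normally be reduced ones.

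All of this lowers the weight of the point. It does not remove it, because none of these safeguards is described as renewing the written instruction about the old bottle.

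Three stronger readings are tempting, and the document supports none of them:
- A reader might infer that participants face seven weeks of unprotected active dosing. Seven is 16 − 9 and includes inert weeks. Other safeguards continue throughout, and nothing shows that an outdated label would lead to double dosing.
- A reader might infer that the label should hold for as long as someone is in the study. Participation runs to six months after session 8, well past the taper.
- A reader might infer from the addendum's kit list, which names no bag, tie or label, that remote participants lack this control. The addendum leaves Benefits and Risks unchanged, so the list's silence is only missing operational detail.

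**Conclusion.** The mismatch is real and minor. On a literal reading, the written warning is shorter than the permitted taper from the second repeated week. For MTcap it is shorter than the active-drug period from the third repeated active week. With two or fewer repeated active packs, no active-drug week falls outside the warning; the 5- or 6-week figures need a near-maximal extension. The result rests on consecutive packs from session 1, on seven active scheduled packs, and on reading the nine weeks as a time limit. Only participants with extended tapers are concerned, and the protocol expects few. The finding is that a stated safety control stops short of the period it should cover, not that anyone is shown to be harmed.

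**What to change.** Keep the label's opening instruction and its exception for staff direction, since the study team may change the dose, including raising it. Replace the time phrase between them with: *while you are on the SWITCH study medication taper, including any extra taper weeks*. The time outside the label's wording then falls from at most 7 weeks to 0.

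Do not tie the label to study participation. Under Care coordination at end of intervention period, the primary care provider is told the final regimen so that monitoring can continue. Hypnotic discontinuation and use at post-treatment and six months are the H2a and H2b outcomes. A study prohibition still standing during follow-up could conflict with that provider's management and would bear on the behaviour being measured, although in both arms.

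This is a cheap improvement. The downside is a reprinted label and a minor amendment.

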Title: Sleep Without Insomnia or The Use of Chronic Hypnotics (SWITCH)

PI: [name], MSHS

NCT number: NCT03687086

Document date: June 19, 2020

SWITCH STUDY PROTOCOL (06.19.2020)

[APPENDIX: "Video/Telehealth Visit Addendum to SWITCH Study Protocol" is at end of document](#)

Design

This is a 5-year multi-site randomized controlled trial that will recruit participants from UCLA Health System and VA Greater Los Angeles.

Setting: To ensure that we meet enrollment targets, the study will include both VAGLA and UCLA Health System. At least 1,200 unique patients at VAGLA have the targeted hypnotics listed in their medical records for at least 3 months within the past 6 months, and 9,100 unique patients at UCLA Health System who receive primary or medicine subspecialty care in the northwest Los Angeles UCLA Health System outpatient clinics have the targeted medications listed within 12 months.

Inclusion/Exclusion criteria:

Inclusion criteria:

- Age > 55 years
- Use of lorazepam, alprazolam, temazepam, clonazepam and/or zolpidem for current or prior insomnia symptoms 2 or more nights per week for at least 3 months
- Current or prior insomnia symptoms
- Available to attend weekly in-person or video sessions over 9 weeks

Exclusion criteria:

High risk for complications in outpatient hypnotic discontinuation program:

- Seizure disorder
- Supratherapeutic or high baseline hypnotic dose (> diazepam-equivalent of 8 mg/night). Note that for individuals on > 1 of the targeted hypnotics, the total baseline hypnotic dose in diazepam-equivalents will be calculated and if > 8 mg/night, individual will be excluded.
- High baseline risk of complicated withdrawal; benzodiazepine intoxication or current or past symptoms of complicated benzodiazepine/alcohol withdrawal (e.g., seizure, delirium at baseline (prior to taper))
- Polydrug use (e.g., chronic high dose opioids)
- Unable to keep study medications in secure location
- Evidence of prescription fraud (e.g., multiple prescriptions for same drug filled at UCLA and non-UCLA pharmacies, diversion)

Discontinuation of hypnotic not appropriate:

- Study-targeted hypnotic used to treat another clinical condition (e.g., panic disorder)

Poor candidate for CBTI:

- Presence of bipolar disorder
- Cognitive impairment (e.g., Mini-Mental State Examination < 24)

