Individuals will be given the choice of having their study visits at UCLA or at either the VA West Los Angeles campus or the VA Sepulveda campus. This option allows individuals to choose the location that is most convenient for them. Individuals who express interest in a VA site will be informed that this choice entails following the VA Research and Development and VA IRB protocol, including signing VA forms, storage of their research data on VA servers and offices, and management of their study medications by VA staff. Individuals who choose to be seen at UCLA will follow the procedures described below. Those who choose to be seen at the VA will be enrolled in the VA study, and will no longer be considered UCLA study participants. Participants seen at the VA will sign a VA consent form and a VA HIPAA Authorization. In addition, they will be asked to sign a UCLA HIPAA Authorization for Research so VA study staff can assess their UCLA medical records to document medications and diagnoses.

In-person screening

Patients recruited directly by study staff in clinic will have the option to complete the screening process in-person with a member of the study team. Patients deemed eligible for participation will be offered to complete the in-person consenting process immediately following the in-person screening (see *in-person consent visit* below for additional information).

In-person consent visit

At the consent visit, potential participants will be shown the wrist actigraph and WatchPat monitoring equipment to ensure that they become familiar and comfortable with this equipment. Capacity to give informed consent will be evaluated with a brief questionnaire (Evaluation to Sign a Consent Form for Research) that asks the participant to recount major procedures and risks of the study. Participants who are unable to provide informed consent will be excluded; proxy consent will not be pursued. Participants who are able to provide informed consent will be asked to sign the written informed consent form and HIPAA authorization and will be provided with copies. A licensed study physician or nurse practitioner will perform the consent procedure.

-Preparation for consent visit:

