We will use an intention-to-treat approach for all analyses. We plan to randomize 188 individuals (including both UCLA and VA sites), of whom we expect 13% to drop out (i.e., fail to complete study assessments) by 6-months, yielding N=164 participants with complete data (~ 82 per group). *We base this drop-out on our completed study ([name] VA Merit 08-295)*. We will include terms for stratification characteristics in all of the models. All analyses below assume $\alpha=0.05$, power=0.80, and two-sided hypothesis tests. Effect sizes are in the measure's natural units and Cohen's d (large=.8; medium=.5; small=.2).

- ***H1: Dysfunctional Beliefs and Attitudes About Sleep – Medication Scale ratings will improve with MTcap compared to SGT+CBTI post-treatment and at 6 months follow-up:***

Analysis: We will fit a 2 (group) by 3 (time) mixed model analysis of variance (ANOVA) model. Interaction terms will be used to assess the change in DBAS medication item (from baseline→post-treatment, baseline→6 months) for MTcap vs. SGT+CBTI group. **Power Analysis:** Based upon our prior research, we estimate the correlation of DBAS scores from baseline to 6-months will be $r=0.55$ (95% CI=0.42-0.65) and the standard deviation will be 2.1. Assuming n=82 per group, the study could detect an effect of 0.9 units on the DBAS-16 scale (Cohen's $d=0.43$). If the baseline to follow-up correlation is $r=0.42$ (95% lower confidence limit [LCL]), the detectable effect size is 1.0 unit on the DBAS-16 scale (Cohen's $d=.47$).

- ***H2a: Participants who receive MTcap will have increased likelihood of hypnotic discontinuation post-treatment and at 6 months follow-up compared with those who receive SGT+CBTI:***

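### The analysis pools UCLA with a separately governed VA study but plans no site term; this costs a little power and leaves chance site imbalance unadjusted, without biasing the treatment contrast

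*Combined protocol and SAP*

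**What the plan says.** The Design section opens with "This is a 5-year multi-site randomized controlled trial", recruiting from UCLA Health System and VA Greater Los Angeles. Under Recruitment, Step 2, site follows the participant's preference: "Individuals will be given the choice of having their study visits at UCLA or at either the VA West Los Angeles campus", or the Sepulveda campus. Those who pick the VA come under VA IRB procedures, VA consent and VA handling of data and study medication. They "will be enrolled in the VA study, and will no longer be considered UCLA study participants".

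The Randomization section names two stratification factors: "Stratified randomization will be used to ensure that both groups are balanced in baseline hypnotic drug type half-life", in three classes, plus gender. On allocation it says that "the data manager will open the next envelope in sequence within the appropriate stratum". It gives 28 per arm and does not say whether UCLA and the VA share one list.

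The section on primary data analysis and power plans 188 randomised over both sites and about 82 per group analysed. Its rule on covariates is "We will include terms for stratification characteristics in all of the models". H2a (discontinuation) uses logistic regression. H1, H2b and H3 use group-by-time terms in mixed models. Neither the primary nor the exploratory plan contains a site term or a site summary. The telehealth addendum changes neither randomisation nor analysis.

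**The concern.** Two separately run studies are combined in every model, and nothing in the models records which study a participant came from. The populations and the day-to-day management may differ, so discontinuation rates or sleep scores may differ too. There are then two possibilities.

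- **One shared list.** Nothing in the design controls how site falls between the arms, and the analysis does not adjust for it.
- **One list per study.** Site is an unstated stratum of the randomisation. The plan's own rule on stratification terms would then call for a site term, and the written models do not name one.

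At stake are precision, power and the match between randomisation and analysis. A colleague will also ask whether the pooled result describes both studies.

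**Working it through.** **Inputs from the documents.** 188 randomised, 13% dropout, 82 per group analysed, 60% vs 80% discontinuation, two-sided alpha 0.05 and power 0.80 (analysis section); 28 per arm (Randomization).

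**Assumptions.** The documents give no UCLA/VA split and no site effect. I take a UCLA share w of 0.298 (56/188, if 28 per arm is the UCLA portion) or 0.50. I take a UCLA–VA difference D in control discontinuation of 0, 10, 20 or 30 points.

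**1. The plan's figure reproduces.** Two proportions, pooled variance, no continuity correction:

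n = [1.96·√(2·0.7·0.3) + 0.842·√(0.24 + 0.16)]² / 0.20² = (1.270 + 0.532)² / 0.04 ≈ 81.2, so 82 per group, with power 0.804. Dropout: 188 × 0.87 = 163.6, or about 164. There is no site component in this.

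**2. H2a without site, as a logistic Wald test.** The log odds ratio is ln(2.67) = 0.981. Its SE is √[1/(82·0.24) + 1/(82·0.16)] = 0.356. Power = Φ(0.981/0.356 − 1.96) = 0.786.

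**3. H2a with site.** Site-specific control rates average 60%, with a common odds ratio chosen so that treated rates average 80%. Within each site, a and c are n·w·p(1−p) for control and treated. Information is the sum over sites of ac/(a+c), and SE = 1/√information.

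Example, w = 0.298 and D = 20 points: control 0.74/0.54, treated 0.887/0.763. Information ≈ 1.61 + 6.02 = 7.63, SE = 0.362, conditional OR 2.74. Power = 0.796.

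| D (points) | Conditional OR | Power with site |
|---|---|---|
| 0 | 2.67 | 0.786 |
| 10 | 2.69 | 0.788–0.789 |
| 20 | 2.74–2.76 | 0.796–0.798 |
| 30 | 2.84–2.90 | 0.808–0.813 |

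Ranges cover w = 0.298 to 0.50.

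**4. Chance imbalance with one shared list.** The SD of the between-arm difference in UCLA share is √[w(1−w)·2/82] = 0.071 to 0.078. A 1.96-SD imbalance multiplied by D shifts the risk difference by 1.4–1.5, 2.8–3.1 or 4.2–4.6 points for D of 10, 20 or 30. For scale, the SE of the risk difference is √(0.40/82) = 7.0 points and the target is 20.

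**5. Type I error without site.** Simulation used 12,000 runs per setting, w = 0.30, and D of 0, 20 or 30 points. The unadjusted test rejected in 0.043–0.049 of runs under both site-blind and site-stratified allocation. The lowest value, 0.043, came with site-stratified lists and D = 30. Monte Carlo SE is √(0.05·0.95/12,000) = 0.002.

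**6. H1, H2b and H3.** The test is a difference in change from baseline. A site main effect γ enters a participant's baseline and follow-up alike, so in the change γ − γ = 0. A few simulated trials of the planned model (82 per arm, 30% UCLA, 0.5 SD site effect) bear this out. With complete data, adding site moved the interaction estimate by less than 1e-14 and left its SE at 0.1579. With 13% missing at 6 months the SE was 0.1670 either way. Only site-by-time can help.

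If site shifts the change itself by D within-site SDs, R² = w(1−w)D²/[1 + w(1−w)D²]. Power = Φ[2.80/√(1−R²) − 1.96] then rises from 0.80 to 0.803–0.804, 0.807–0.809 or 0.820–0.823 for D of 0.2, 0.3 or 0.5.

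**The case against.** The strongest reply is that the numerical effect is small and rests on an undocumented site effect. That stands. Up to a 20-point site difference the H2a gain is about one power point. It does not come from a smaller SE: at a 30% UCLA share the SE of the log odds ratio rises from 0.356 to 0.358, 0.362 and 0.368 for differences of 10, 20 and 30 points. The gain comes from the conditional odds ratio lying further from 1. Linear-model reasoning about standard errors that are too wide does not carry over to H2a.

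Chance imbalance is also ordinary sampling variation, already carried in the SE. A 1-SD shift, 0.7 to 2 points at a 30% share, is small beside an SE of 7.

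It may further be said that the VA study's own protocol could specify separate lists, so that site is controlled by design. That is possible, but the documents do not say so, and the analysis would then omit a stratum that the plan's rule implies should be modelled.

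Stronger readings are tempting and are not supported:

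- **Self-selection of site biases the comparison.** The choice precedes randomisation, so it cannot.
- **Site is the largest, or a known prognostic, grouping.** No split and no site effect is given.
- **Remaining randomisations should be stratified by site.** This is redundant if lists are already separate. Otherwise it takes 6 strata to 12 mid-trial, about 16 participants each on average (188/12), with some likely sparser.

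**Conclusion.** The omission is real and modest. The plan pools two separately governed studies, adjusts only for half-life class and gender, and does not say how allocation relates to site. The treatment contrast is not biased, type I error is not inflated, and the sample size is not in error.

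For H2a the loss of power is nil if site has no effect, about 1 point or less up to a 20-point site difference, and 2 to 3 points at 30. These figures rest on an assumed UCLA share of 30–50% and assumed site effects. For H1, H2b and H3 a gain is possible only if site affects change over time and site-by-time is modelled. The unresolved 56 against 188, and the unstated number of lists, are gaps whatever the site effect proves to be.

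**What to change.** 1. Define site as the enrolling study, UCLA or VA. Visit location will not serve: the protocol allows sessions for UCLA participants at VA campuses, and the addendum adds remote visits.
2. Add site as a fixed term in the H2a logistic models, beside half-life class and gender.
3. In the H1, H2b and H3 mixed models add site and site-by-time.
4. State whether there is one randomisation list or one per study, and reconcile 28 per arm with 188 in total.

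Leave the stratification scheme as it is. The cost is a few sentences and a variable already held: one degree of freedom in H2a, and three in a three-time-point mixed model (one for site, two for site-by-time). The H2a odds ratio becomes conditional on site as well as on the stratification factors, and the report should say so. No new data and no change in sample size are needed. The terms should be fixed before any analysis by arm.
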